## 5.5. Participant withdrawal

Each participant has the right to withdraw at any time. The data will be collected in an pseudonymised format. This means that a participant can withdraw from the study. In order to withdraw from the study a participant will need to contact the Chief Investigator. This will be explained in the participant information sheet.

# 6. Assessment

## 6.1 Definition of end of trial

The end of the trial will be when the required number of anaesthetists have completed the web-based test for the validation phase of the study. The data will then be locked for analysis.

## 6.2 Likely rate of loss to follow up

Losses to follow up are expected to be very few, as each participant will be expected to complete the online test in one sitting. However, in the case of individuals failing to complete the test (e.g. registered but did not take the test, attempted too few questions), their scores will be excluded from the final analysis. We will build an expected loss to follow up of 10% when powering the study.

## 6.3 Expenses

Participants will not be paid expenses for taking part.

# 7. Statistics and Data Analysis

## 7.1 Sample Size Calculation

Sample size for the definitive data capture stage, 'Phase 5 – Psychometric main study testing', will be calculated using a power calculation based on data obtained in the pilot work during 'Phase 3 – Preliminary testing'. For example, internal reliability of the item responses is to be assessed using Cronbach's alpha, an alpha value of 0.70 being considered adequate. With 250 participants completing a 50-item questionnaire it would be possible to show that Cronbach's alpha is significantly higher than 0.6 if the true value is 0.7 i.e. there is

a greater than 85% chance (power) that the 95% confidence interval for Cronbach's alpha will exceed 0.6 and include 0.7.

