### 3. Study Design

This is a prospective, multi-centre study leading to the identification of a validated, reliable and defensible assessment tool for assessing UGRA image interpretation.

Study population	Anaesthetists in the UK
Inclusion	Registered in an approved UK anaesthetic training programme Anaesthetic consultants on the GMC register
Exclusion(s)	Staff grade, associate specialist and specialty doctors not enrolled in a UK anaesthetic training programme
Sample size	Pilot phase: 35-50      Study phase: 250
Duration	12 months
Study centres	Imperial College Healthcare NHS Trust, London  Royal Gwent Hospital, Aneurin Bevan University Health Board, Wales  Southern Health and Social Care Trust, Northern Ireland, UK  Belfast Health and Social Care Trust, Northern Ireland, UK  NHS Greater Glasgow & Clyde, Scotland, UK  Guy's & St Thomas NHS Foundation Trust, London, UK  Frimley Health NHS Foundation Trust, UK
Primary outcome	A validated, reliable and defensible assessment tool to test ultrasound-guided regional anaesthesia image interpretation skills
Secondary outcome(s)	The secondary outcomes are development a validated, reliable and defensible assessment tool assessing anatomical, clinical knowledge and the performance of ultrasound guided regional anaesthesia: 

• Assessment of anatomical knowledge relevant to performing a local anaesthetic injection around peripheral nerves

• Assessment of clinical regional anaesthesia knowledge relevant to performing a local anaesthetic injection around peripheral nerves

• Assessment of the performance of an ultrasound-guided local anaesthetic injection around peripheral nerve

This study will have 5 Phases:

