The internal reliability of the item responses will be assessed using Cronbach's alpha. An alpha value of 0.70 will be considered sufficient and acceptable for the questions. A split-test method will also be used for each participant to compare the first half of their assessment with the second half to ensure internal consistency of their item responses. The difficulty index calculated for items in the pilot study will be used to ensure a balanced set of test items, in terms of their difficulty, in the first and second halves of the test. All items will be made mandatory. The test will be administered by local investigators via a web-based application. It will have an automatic system of marking to minimise inter-marker differences. It will also be manually checked by investigators who are blinded to the level and identity of the participant. We will aim to recruit a minimum of 250 participants so that there is a stable reliability value, each of whom will be allocated a participant number to pseudonymise the data. The results will be analysed only when recruitment has ended.

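### The Phase 5 sample size is 250 in sections 3 and 3.5 but still to be calculated from the pilot in section 7.1, and the plan does not settle whether 250 counts people recruited or tests completed

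*Combined protocol and SAP*

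**What the plan says.** Five places in the combined protocol and SAP bear on the Phase 5 size.

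- **Section 3 (design table):** "Study phase: 250".
- **Section 3.5:** "We will aim to recruit a minimum of 250 participants so that there is a stable reliability value". This counts people recruited.
- **Section 7.1:** the size "will be calculated using a power calculation based on data obtained in the pilot work during" the preliminary testing phase. The figure of 250 then appears in a worked example, which opens "With 250 participants completing a 50-item questionnaire it would be possible to show". This counts people who complete. The result claimed for them is "Cronbach's alpha is significantly higher than 0.6 if the true value is 0.7". The example is restated as "a greater than 85% chance (power) that the 95% confidence interval for Cronbach's alpha will exceed 0.6 and include 0.7".
- **Section 6.2:** scores from people who do not complete the test are excluded, and a 10% loss is to be allowed for in the powering.
- **Section 6.1:** "The end of the trial will be when the required number of anaesthetists have completed the web-based test", after which the data are locked. No figure is given.

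Section 3.3 sets the pilot at 35-50 people and says it will be used to remove poorly discriminating items. It also says the pilot test will have more items than the final one.

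**The concern.** The number in section 6.1 decides when the trial ends and the data are locked, and section 3.5 holds the analysis until recruitment has ended. A reader cannot tell from the plan whether that number is 250 or a figure the pilot will supply, or whether a pilot result may raise, lower or replace 250. Nor can a reader tell whether 250 already contains the 10% allowance, since 3.5 counts recruits and 7.1 counts completers.

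Three things are at stake:

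- The end-of-trial trigger is not fixed in the document.
- The stated power can be missed if 250 is read as the recruitment target.
- If the pilot alpha is what feeds the calculation, the Phase 5 size would be driven largely by sampling error in a small pilot of a longer, unpruned test.

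Section 7.1 also joins two different events by an i.e.: alpha being significantly above 0.6, and the interval lying above 0.6 while containing 0.7.

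**Working it through.** **Inputs.** From 7.1: n = 250 completers, k = 50 items, reference alpha 0.6, true alpha 0.7, 95% interval, stated power above 85%. From 6.2: 10% loss. From 3.3: pilot of 35-50.

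**Step 1: reproduce the plan's figure.** Under Feldt's result, W = (1 − α)/(1 − α̂) follows F(n − 1, (n − 1)(k − 1)). The lower 95% limit is 1 − (1 − α̂)·F₀.₉₇₅. With true alpha 0.7 it exceeds 0.6 when W > (0.3/0.4)·F₀.₉₇₅.

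- n = 250: the distribution is F(249, 12,201), with F₀.₉₇₅ = 1.1854. The threshold is 0.75 × 1.1854 = 0.8891, and P(W > 0.8891) = 0.894.
- The event as worded also needs the interval to contain 0.7. The interval lies wholly above 0.7 with probability 0.025, so the joint probability is 0.8935 − 0.025 = 0.869. (An interval wholly below 0.7 needs W < F₀.₀₂₅ = 0.8307, which the first condition already excludes.)
- Cross-check with Bonett's approximation: √((n − 2)(k − 1)/(2k))·ln(0.4/0.3) − 1.96 = √(248 × 49/100) × 0.2877 − 1.96 = 1.211, which gives 88.7% for the lower limit alone.

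Both events support the stated figure. The smallest n for 85% is 217 (lower limit alone) or 235 (event as worded), so 250 completers is enough.

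**Step 2: recruited or completed.** 250 × 0.9 = 225 completers; 250/0.9 = 277.8, so 278 recruits are needed for 250 completers.

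- n = 225: the distribution is F(224, 10,976), with F₀.₉₇₅ = 1.1960. The threshold is 0.8970. The lower limit exceeds 0.6 with probability 0.862, and the event as worded has probability 0.8619 − 0.025 = 0.837.

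| Completers | Lower limit above 0.6 | Event as worded in 7.1 |
|---|---|---|
| 250 | 89.4% | 86.9% |
| 225 | 86.2% | 83.7% |

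**Step 3: sizing from the pilot.** Assumption: the pilot alpha is entered as the true value against 0.6, with 50 items and 85% power for the lower limit. The plan does not say this. The smallest n, by pilot alpha, is:

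| Pilot alpha | Required n |
|---|---|
| 0.60 or less | none |
| 0.65 | 1,016 |
| 0.68 | 362 |
| 0.70 | 217 |
| 0.72 | 141 |
| 0.75 | 81 |
| 0.80 | 38 |

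The spread of pilot alpha at a true alpha of 0.70 comes from the same F distribution:

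| | Pilot of 35 | Pilot of 50 |
|---|---|---|
| Quartiles of pilot alpha | 0.637 to 0.740 | 0.650 to 0.734 |
| Required n at those quartiles | about 1,930 to 97 | about 1,020 to 108 |
| Pilot alpha below 0.6, no n exists | 15% | 10% |

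The chance that the calculation asks for more than 250 or has no solution depends on the true alpha:

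| True alpha | Pilot of 35 | Pilot of 50 |
|---|---|---|
| 0.70 | 50% | 49% |
| 0.75 | 24% | 19% |
| 0.80 | 6% | 3% |

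The results are almost unchanged if the pilot has 80 items.

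**The case against.** Much can be said for the plan.

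- **250 and a minimum of 250 are compatible.** This stands. Read together they make 250 a floor, and a smaller pilot-based answer would simply give way to it. The conflict is only with 7.1, where 250 is an example.
- **The plan states no pilot-alpha rule.** This stands. Pilot data could instead inform the number of items kept or the between-group variance for the ANOVA. A reader might infer that the 7.1 approach yields unusable sizes or none. The documents do not support that. Even under the assumption, a pilot alpha near 0.70 gives about 217, and a solution is missing only at or below 0.6. The result is unstable, not useless.
- **The requirement to contain 0.7 describes the example.** This largely stands. A reader might infer that a more reliable test would count as a failure, since at 250 completers the joint event has probability 46% at a true alpha of 0.75 and 0.7% at 0.80. But 7.1 conditions the sentence on a true value of 0.7, and sections 3.5 and 7.3 call 0.70 sufficient. No passage treats a higher alpha as a miss. What remains is that two different events are presented as one.
- **The pilot is analysed before Phase 5 (7.3.1), so the number could be settled in time.** True, but the plan does not say that it will be, or how.
- **Barring all use of pilot data would be a preference.** Fair. An increase for the group comparison would be consistent with 250 as a floor, if the plan named it.

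None of this answers the recruited-versus-completed ambiguity or the missing figure in 6.1.

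**Conclusion.** The concern holds as an unresolved sample size, not as a wrong one. Section 7.1 leaves open a number that sections 3 and 3.5 already state, and 6.1 relies on it without naming it. The arithmetic in 7.1 is sound for 250 completers (86.9% for the event as worded). It falls to 83.7%, just under the stated figure, if 250 are recruited and 10% are lost; the lower-limit event alone would still be met with 86.2% probability.

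That a pilot of 35-50 cannot reliably set the size rests on the assumption that its alpha would be plugged into the 7.1 example. How often that would ask for more than 250, or fail, depends strongly on the true alpha: about half of pilots at 0.70, 19-24% at 0.75 and 3-6% at 0.80. All power figures assume Feldt's distribution and 50 items. The plan should be reconciled before Phase 5 recruitment opens.

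**What to change.** 1. State one number in sections 3, 3.5, 6.1 and 7.1: 250 completed Phase 5 tests, with a recruitment target of about 278 under the 10% loss in 6.2. In 6.1, put that number in place of the unspecified one.
2. In 7.1, replace the statement that the size is to be calculated from pilot data. Say that 250 completers is justified by the worked alpha calculation and that the pilot alpha will not be used to lower or replace it. If an increase for another analysis is wanted, name the pilot quantity and settle the number before Phase 5 recruitment starts.
3. In 7.1, drop the requirement that the interval also contain 0.7. State instead that the lower 95% limit exceeds 0.6 with probability about 89% at a true alpha of 0.70, with 250 completers and 50 items (about 86% if only 225 complete).

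The cost is wording. About 28 more people (278 − 250) are needed only if the allowance promised in 6.2 was not already inside the 250. If they cannot be added in an unfunded 12-month study, keep 250 recruited, say so in all four sections, put 225 expected completers in 6.1 and 7.1, and state the 86% figure. The sponsor gives up the option of resizing downward on the pilot alpha, which 35-50 people cannot support.

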### 7.3.1 Frequency of analyses

The primary analysis will take place when the pilot study recruitment is complete in phase 3. This will be used to guide the generation of the final version used in the next phase. Then the analysis of the phase 5 validation study will take place when recruitment for this test is complete. No interim analysis is planned.

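### Does planning 10% loss against a recruitment minimum of 250 undercut the power stated in section 7.1?

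*Combined protocol and SAP*

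**What the plan says.** Section 7.1 says that the Phase 5 sample size "will be calculated using a power calculation based on data obtained in the pilot work". It then gives an illustration, introduced as an example: "With 250 participants completing a 50-item questionnaire it would be possible to show" that alpha is above 0.6 if its true value is 0.7. The event is defined as a 95% confidence interval that lies above 0.6 and includes 0.7, and its probability is put at more than 85%.

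Section 3.5 states: "We will aim to recruit a minimum of 250 participants so that there is a stable reliability value". The design table in section 3 lists 250 for the study phase without saying whether these are people registered or people completing.

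On loss, section 6.2 expects very little because the test is taken in one sitting. It drops the scores of people who register but do not take the test, or who answer too few questions, and adds: "We will build an expected loss to follow up of 10% when powering the study".

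On timing, section 6.1 says: "The end of the trial will be when the required number of anaesthetists have completed the web-based test" for the validation phase, followed by "The data will then be locked for analysis". Section 3.5 says: "The results will be analysed only when recruitment has ended". Section 7.3.1 says: "Then the analysis of the phase 5 validation study will take place when recruitment for this test is complete".

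**The concern.** The same 250 appears as a count of completers in 7.1 and as a count of recruits in 3.5. Section 6.2 makes clear that these groups can differ, since some who register will be left out of the analysis. A 10% allowance is promised, yet no larger number to register is printed anywhere.

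The timing statements seem to add to the difficulty. Section 6.1 works from completed tests, while 3.5 and 7.3.1 work from the end of recruitment. A reader who takes 3.5 and 7.3.1 alone could close recruitment at 250, lose a tenth, and analyse 225. The probability in 7.1 would then no longer hold at the protocol's own loss rate, and the listed centres could differ on when to stop recruiting.

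**Working it through.** **Inputs.** From 7.1: n = 250 completers, k = 50 items, true alpha 0.70, comparison value 0.60, 95% interval. From 6.2: 10% loss. Assumption: the interval is two-sided and computed by Feldt's method, because 7.1 states neither.

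**Method.** W = (1 − α)/(1 − α̂) follows an F distribution with n − 1 and (n − 1)(k − 1) degrees of freedom. Let U be its 97.5% point.

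- The lower confidence limit is 1 − (1 − α̂)U. It exceeds 0.6 when W > (0.30/0.40)U = 0.75U.
- The interval also includes 0.7 unless W > U (whole interval above 0.7) or W is below the 2.5% point. The latter is already ruled out by the first condition.
- So P(joint event) = P(W > 0.75U) − 0.025.

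**The plan's own figure, n = 250.** Degrees of freedom are 249 and 249 × 49 = 12,201. U = 1.1854 and 0.75U = 0.8891. P(W > 0.8891) = 0.8935, so the joint probability is 0.8935 − 0.025 = 0.8685. The statement of more than 85% is reproduced. Simulation gives 0.869, and Bonett's approximation gives 0.862.

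**The feared case, n = 250 × 0.90 = 225.** Degrees of freedom are 224 and 10,976. U = 1.1960 and 0.75U = 0.8970. P(W > 0.8970) = 0.8619, so the joint probability is 0.8369. The gap to 85% is 1.3 points.

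| Completers | Lower limit above 0.6 | Joint event in 7.1 |
|---|---|---|
| 225 | 86.2% | 83.7% |
| 234 | 87.4% | 84.9% |
| 235 | 87.5% | 85.04% |
| 250 | 89.4% | 86.9% |
| 278 | 92.1% | 89.6% |

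**Loss that 250 registrations can absorb.** The joint probability stays above 85% down to 235 completers, so up to (250 − 235)/250 = 6% may be lost with no inflation at all. With exactly 10% expected loss and independent completion, P(at least 235 of 250) = 1.8%, so the full 10% would indeed take the study below that point.

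**Sensitivity.** With a one-sided 95% bound, the joint event has probability 86.6% at 225. With Bonett's interval instead of Feldt's, the 225 figure is 82.8%. The choice of interval method therefore moves the result by 0.9 points, which is close to the size of the shortfall itself.

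**What the plan's own steps give.** Adding the 10% promised in 6.2 to a target of 250 completers gives 250/0.90 = 277.8, so 278 registrations. That yields 250 completers only on average (57% chance of at least 250), but the completer count in 6.1 covers the remainder, because the study ends when enough people have finished.

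**The timing statements side by side.** Section 3.5 sets a floor on recruitment and bars analysis before recruitment ends. Section 7.3.1 says the same about the order of events. Neither says what closes recruitment. Section 6.1 does: the required number of completed tests. The three can be followed together by recruiting at least 250, stopping when enough have completed, locking the data and analysing.

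**The case for a change.** The strongest case for a change is that the two readings of 250 fall on opposite sides of the protocol's own 85%. Section 3.5 states its 250 as a working aim and not as an illustration. Sections 3.5 and 7.3.1 do not themselves say that recruitment stays open until enough people have finished. Since the pilot-based calculation is still to be done, it could inherit the ambiguity, and a sentence or two would remove it.

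Part of this stands. The number 250 does serve for two different counts, and the 10% is not yet visible in any figure. The numbers for 225 are also correct.

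It does not follow that the plan is wrong. Reaching 225 takes four steps together: recruitment closes exactly at a stated minimum, the completer-based end in 6.1 is ignored, the allowance in 6.2 is never added, and the full 10% is lost although losses are expected to be very few. A final number to register could not be printed before the pilot in any case, because 7.1 makes the sample size depend on pilot data.

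**Conclusion.** The concern does not call for a change. Section 7.1 contains no arithmetic error: for 250 completers the probability is 86.9%, as claimed. What remains is a detail not yet filled in, namely whether the recruitment figure in 3.5 already includes the loss allowance. Sections 6.1, 6.2 and 7.1, followed as written, lead the analyst to the sensible answer: count completers, add 10%, and set the number after the pilot.

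In the least favourable reading the joint probability is 83.7%, a shortfall of 1.3 points. The joint event loses 2.5 points to samples whose whole interval lies above 0.7, which would be favourable results for the test. The substantive aim, showing alpha above 0.6, keeps 86.2% power at 225. No conclusion of the study would change.

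These figures assume 50 items, a true alpha of 0.70 and a two-sided Feldt interval.

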## 7.2 Trial Methods

### 7.2.1 Blinding

The investigators will be blinded to the level of training when checking the automatic marking of the test answers.

### 7.2.2 Measures taken to avoid bias

All tests will be anonymised and marked automatically by the web-based application to avoid bias. Answers will be checked by local investigators, who will be blinded to the identity of the participant.

It is important to recognise that due to the change in the RCoA curriculum, some participants will be familiar with the CRQ format while others might be more familiar with MCQ-based format, or other forms of assessment question. Participants in the pilot and main study will be provided with sample questions and answers prior to the test to familiarise themselves with the question format.

## 7.3 Plan of Analysis

We have taken advice from the Imperial College statistician, [name] [name].

The primary outcome will be analysed using a series of calculated indices and statistical tests. A difficulty index will be calculated by dividing the number of correct responses by the total number of responses, with a difficulty index  $<50\%$  considered sufficient to exclude an item from the test. Content validity will be calculated by asking an expert panel to rate items in the test on a 4-point scale as definitely not suitable, probably not suitable, probably suitable and definitely suitable. A validity index of  $> 0.78$  will be considered sufficient to include a question. Construct validity will be measured using a one-way analysis of variance (ANOVA)/Rasch modelling, internal reliability using Cronbach's alpha (with a value of 0.70 considered sufficient), and internal consistency using a split-test method.

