Consistency of measurement or **reliability** is essential in the assessment tool. **Cronbach's alpha method** is commonly used to assess internal consistency reliability. We will use also use a “**split-half**” method of comparison in the final version of the test wherein the performance of the same participant in the first half is compared to their performance in the second half. The optimal test length is a balance. Using more test items produces more measurements of the construct and therefore result in higher reliability. This must be set against potential cognitive fatigue and participant drop out with longer test times. Statistical analysis of the pilot testing will allow items with higher discrimination to be kept in the final version of the test and lower discrimination, or lower measurement value, to be removed. Inter-rater or marker variability can be minimised by a system of automatic computer marking. However, the marking will also be corroborated by manual checking by investigators blinded to the participant’s training level and experience.

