### 3.3 Phase 3 – Preliminary testing

The pilot test will be administered by local investigators via a computer-based application (<https://www.classmarker.com/>) to 35-50 trainees and consultants, recruited by email and flyers sent to schools of anaesthesia across the UK. The cohorts will include an equal number of trainees and consultants of varying experience, based on the new RCOA curriculum and the extent of their regional experience (stage 1 (CT1-3); stage 2 (ST4-5); stage 3 (ST6-7); stage 3 + regional fellowship trained; consultant; consultant with special interest in regional; consultant + regional fellowship trained). The pilot test will contain short video clips and images of ultrasound guided regional anaesthesia with questions in a constructed response question (CRQ) format to identify relevant structures, anatomy and clinical knowledge. It is important to recognise that due to the change in the RCoA curriculum, some participants will be familiar with the CRQ format while others might be more familiar with MCQ-based format, or other forms of assessment question. Participants in the pilot and main study will be provided with sample questions and answers prior to the test to familiarise themselves with the question format.

Face validity of the test will also be assessed by asking participants to comment on the ease of understanding and to identify terms that appear ambiguous. Participants will be able to comment in a text box after each item in the questionnaire. They will also be asked to comment on how they would improve the test and any relevant anatomy or clinical

knowledge missing from the questions. The format of the test will be amended based on the comments.

A difficulty index of each item will be calculated by dividing the number of correct responses by the total number of responses, as detailed in Abubakar *et al*'s study, and thus a higher value suggests a question is easier to answer. Any item with a difficulty index of < 50% will be considered too difficult to answer by the respondents and will be considered for removal. This will be compared to the information gathered from the panel of experts on test items, for example whether the anatomical structure is essential, desirable, expert or not relevant to the specific ultrasound guided nerve block.

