One important step in establishing construct validity is to use the pilot study to identify how well the answers for each test item discriminate between the participant's level of ultrasound experience. Differences in ultrasound interpretation skills between study groups will be analysed using one-way analysis of variance (ANOVA)/Rasch modelling. Items that discriminate well will be retained and those that discriminate poorly will be removed from the main test.

Reliability of the test will be improved by presenting the pilot test items in a random order to minimise any effect of cognitive fatigue diminishing performance on subsequent items. The average time taken for participants to complete each item in the pilot test will also be recorded to guide the optimal final study test length. It is important to balance the maximum number of test items whilst minimising the risk of cognitive fatigue and participant drop out. While the pilot test will necessarily have more items than the final test, pilot test participants will be asked to comment on the point at which they felt fatigued to guide this balance. It will also be important to understand whether level of regional anaesthesia experience affects fatigability.

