### 3.4 Phase 4 – Testing for content validity

To ensure all items in the assessment tool have the content that tests the domain we intend to test, following the pilot the amended test will be presented to the panel of 5 experts in regional anaesthesia, who will be asked to rate the suitability of ultrasound images and questions to performance of the block. This will be on a 4-point Likert scale (1 = definitely not suitable, 2 = probably not suitable, 3 = probably suitable, 4 = definitely suitable).

The content validity of each item will be calculated by dividing the number of experts who rated the item as suitable and very suitable (3 and 4 on the scale) by the total number of experts. Items found to be appropriate by a sufficiently high percentage of participants will be selected. For example, if 26 out of 40 (65%) participants rate an item as suitable or very

suitable then the lower 95% confidence limit for this proportion is 51%, indicating that more than 50% of experts are likely to find it appropriate.

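### Section 7.3 lets a difficulty index below 50% exclude an item on its own, while section 3.3 only reviews such an item and keeps those that discriminate well

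*Combined protocol and SAP*

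**What the plan says.** Three statements in the current text govern what happens to a hard pilot item.

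- **Section 7.3, Plan of Analysis.** The index is the number of correct responses divided by all responses. A value below 50% is "considered sufficient to exclude an item from the test". No other condition is attached.
- **Section 3.3, Phase 3, on difficulty.** An item below 50% is "considered too difficult to answer by the respondents and will be considered for removal". The text continues: "This will be compared to the information gathered from the panel of experts on test items", meaning the classification of the structure as essential, desirable, expert or not relevant. It gives no rule for deciding after that comparison.
- **Section 3.3, Phase 3, on discrimination.** "Items that discriminate well will be retained and those that discriminate poorly will be removed from the main test". There is no exception for hard items and no threshold. Section 1.1 agrees: pilot analysis is to allow "items with higher discrimination to be kept in the final version of the test".

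The pilot has 35 to 50 participants in seven listed experience groups, four of trainees and three of consultants: "The cohorts will include an equal number of trainees and consultants of varying experience". Section 7.3.1 says only that the pilot analysis will guide the final version. No section ranks difficulty against discrimination.

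**The concern.** The index pools everyone from stage 1 trainees to fellowship-trained consultants. An item that most non-experts miss and most experts answer can therefore fall below 50% because it separates the groups. Section 7.3 treats that item as too hard to keep; section 3.3 treats it as one to retain.

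The choice of rule decides which items enter the Phase 5 test. The Study Summary gives the aim as telling users of different skill levels apart reliably, and construct validity in sections 1.1 and 3.5 rests on experienced anaesthetists scoring higher. The items at risk serve that aim, mainly at the senior end. Defensibility is also part of the primary outcome, and two item-selection rules that can give opposite answers are hard to defend.

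**Working it through.** The plan states no figure on this point, so there is none to reproduce. The question is whether one item can meet both rules, and under what conditions.

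**Inputs.** From section 3.3: seven groups, 35 to 50 participants, index = correct / total, one-way ANOVA named for group differences. I take 5 or 7 per group (n = 35 or 49). The three regionally experienced groups are stage 3 with fellowship, consultant with special interest, and consultant with fellowship. All correct-answer rates below are assumptions.

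**1. Perfect separation.** All three experienced groups correct, nobody else:
- equal groups: 15/35 = 21/49 = 42.9%;
- half trainees and half consultants, with equal groups within each half: experienced share = 1/8 + 1/6 + 1/6 = 45.8%.

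Both are below 50%, so 7.3 allows exclusion of an item that discriminates perfectly. This example needs no significance cut-off.

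**2. A less extreme item, 5 per group.** Correct answers 5, 5, 4 (experienced) and 1, 1, 1, 0 (others). The index is 17/35 = 48.6%.
- Between groups: (25 + 25 + 16 + 1 + 1 + 1 + 0)/5 − 17²/35 = 13.80 − 8.26 = 5.54, on 6 df.
- Within groups: 17 − 13.80 = 3.20, on 28 df.
- F = (5.54/6)/(3.20/28) = 8.08, P = 0.00004.

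**3. A gradual gradient, 7 per group.** Correct answers 1, 1, 2, 4, 4, 6, 6. The index is 24/49 = 49.0%; F = 3.34, P = 0.009.

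**4. How often the rules would collide for a single item.** Pooled index = (k·e + (7 − k)·r)/7, with k experienced groups at rate e and the rest at r. The last column is the simulated chance (200,000 draws) that the index is below 50% and the seven-group ANOVA gives P < 0.05. That cut-off is assumed, because section 3.3 gives none.

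| Item (experienced v others) | k | True index | Phi | Conflict, n = 35 / 49 |
|---|---|---|---|---|
| 90% v 15% | 3 | 47% | 0.74 | 0.69 / 0.73 |
| 80% v 20% | 3 | 46% | 0.60 | 0.61 / 0.73 |
| 90% v 30% | 2 | 47% | 0.54 | 0.53 / 0.64 |
| 90% v 30% | 3 | 56% | 0.60 | 0.18 / 0.15 |
| 45% in every group | – | 45% | 0 | 0.04 / 0.04 |

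Conflict is common when an item discriminates strongly and its pooled index lies just under 50%. The fourth row discriminates as strongly as the second by phi; it conflicts less often because its index is above the cut.

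**5. Could seven-group ANOVA P < 0.05 define good discrimination?** Section 3.3 also removes poor discriminators, so that cut-off would become a removal rule. Chance of reaching P < 0.05 at n = 35 / 49:
- 90% v 30%, k = 3: 0.84 / 0.95;
- 70% v 30%, k = 3: 0.39 / 0.53;
- graded 20, 30, 40, 50, 50, 60, 70%: 0.25 / 0.34.

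It would miss many items with a real gradient.

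**The case against.** The best defence is that sufficiency in 7.3 only permits exclusion. On that reading 7.3 is a short summary, 3.3 is the detailed procedure, and being open to exclusion is close to being considered for removal. This softens the clash with the difficulty sentence of 3.3. It does not remove the clash with the discrimination sentence, because a permission to exclude still conflicts with a statement that good discriminators are retained. It also leaves the choice open until pilot results are known.

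Two further objections stand. Section 3.3 sets no threshold for good discrimination, offers ANOVA or Rasch modelling, and does not say that the ANOVA is done item by item. A reader might infer from the worked item that 3.3 certainly keeps it. That holds only under an assumed cut-off, although F = 8.1 would meet any usual one and perfect separation needs none. The high-conflict examples also all have true indices just under 50%, so they show that the conflict can happen, not how often it will.

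A reader might also infer that the content validity index above 0.78, which "will be considered sufficient to include a question", competes with the difficulty rule without any order. The documents do not support this. Section 3.4 places that rating later: "following the pilot the amended test will be presented to the panel of 5 experts". Items dropped after the pilot, for whatever reason, are simply not rated at that stage.

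**Conclusion.** Wrong as written: the item-selection rules in 7.3 and 3.3 contradict each other, and one item can meet both. Severity is low to moderate.

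That such items can exist follows from the pooled index and the seven-group design. How many there will be depends on item difficulties that the documents do not give, so it cannot be estimated. The probabilities in the table rest on assumed answer rates and an assumed P < 0.05.

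A stronger reading would be that the finished test will fail to discriminate or will be unreliable. The documents do not support that. Many items would be unaffected, the loss would fall mainly at the senior end, and the overall ANOVA and Cronbach's alpha would probably change little. Nor does 7.3 say that every item below 50% must go; the fault is that it lets the index decide alone where 3.3 does not.

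**What to change.** Before pilot items are selected, reword 7.3 to match 3.3, for example:

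> An index < 50% flags an item for review against the panel category and its discrimination between experience groups; no item is removed on the difficulty index alone, and an item that discriminates well is retained as in 3.3.

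State the discrimination measure and its cut-off in both sections before pilot data are seen. An effect-size or ordered measure is preferable, such as an item-total correlation, a correlation of item score with experience level, or a Rasch measure. A seven-group ANOVA at P < 0.05 is a poor choice: it has low power with 5 to 7 people per group and ignores the order of the groups.

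The cost is wording only, since the pilot responses, group comparison and panel categories are already planned. There are two downsides. The test may be somewhat harder for junior trainees, and any discrimination estimate from 35 to 50 people is imprecise, so some items will still be misjudged.
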